Those who choose virtual visits will self-collect a nasal swab and a Mitra kit blood sample and send then to the appropriate location. At the convalescent visit, subjects will self-collect and send in a Mitra kit blood sample.

At the first ILI visit study coordinators will record ILI history, hospitalizations status, and work days lost. At the second ILI visit during the convalescent phase of liness, coordinators will collect updated information on hospitalization status and work absences. This information will be collected at both the in-person and virtual visits.

All subjects will also be asked for permission to review their recorded medical encounters in order to ascertain whether they sought care for influenza-like illness. The test results will be for research purposes and will not be used to guide case management.

Immunogenicity substudy: Up to 1200 subjects (approximately 400/arm) from the main study will be enrolled in a vaccine immunogenicity substudy. Substudy participants will have blood drawn up to 30 days prior to vaccination and then approximately one month post-vaccination in order to compare the effect of the vaccines on humoral and cellular immune responses.

End of study self-collected Mitra kit: Approximately 1,000 subjects who develop an ILI will be asked to collect and send in a self-collected Mitra blood kit. These individuals will be selected from the groups who completed the substudy or the same-day/post-vaccination blood sampling.

Study Period: Oct 2018 – Sep 2023

Enrollment: Oct 2018 –Dec 2018, Sep 2019- Jan 2020, Sep 2020-Jan 2021, Sep 2021- Jan 2022
Influenza-like illness (ILI) surveillance: Oct 2018 – May 2019, Sep 2019 – May 2020, Sep 2020-May 2021, Sep 2021-May 2022

Analysis/Interpretation: May 2019 - Sep 2023

9.2 Key Words:

Provide up to 5 key words that identify the broad topic(s) of your study

influenza, vaccine, effectiveness, immunogenicity, antibody

9.3 Background and Significance:

Include a literature review that describes in detail the rationale for conducting the study. Include descriptions of any preliminary studies and findings that led to the development of the protocol. The background section should clearly support the choice of study variables and explain the basis for the research questions and/or study hypotheses. This section establishes the relevance of the study and explains the applicability of its findings

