- Demographics (source: patient-completed quiestionnaire)
 - ° age
 - sex
 - ° weight

- height
- ethnicity
- ° race
- DEERS status (active duty, retiree, beneficiary)
- Military rank (active duty only)
- Subject may opt-in for a same-day and post vaccination self-collected blood sample using a Mitra Device. If they opt-in, their first sample will be taken the same day as their vaccination and their second sample will be taken 14-30 days later. Subjects may be asked to provide an end of study mitra kit.

Immunogenicity substudy subjects only

Study Day -30-0

• Venipuncture blood draw (approximately 40 mL)

Study Day 21-35

• Venipuncture blood draw (approximately 40 mL)

Acute Influenza-like Illness Surveillance

The main study will rely on the identification/ascertainment of individuals with acute ILI. During the ILI surveillance period, subjects will receive an automated email or text message (via REDCap platform) at 1 week intervals asking them if they have experienced ILI in the preceding 7 days. Subjects will get a reminder email or text 72 hours later and again 24 hours later if they have not responded to the weekly ILI surveillance. Influenza-like Illness (ILI) will be defined as:

- Cough OR sore throat AND
- Feverish/Chills OR Body aches/fatigue

The email or text messages (sent on a weekly basis) will also remind subjects to contact their medical provider should they experience any of the emergency signs described on the CDC's influenza website (https://www.cdc.gov/h1n1flu/homecare/warningsigns.htm, (Kellerman AL et al. Webbased self-triage of influenza-like illness during the 2009 H1N1 influenza pandemic. Ann Emerg Med. 2010 Sep;56(3):288-294). They are:

- Difficulty breathing or shortness of breath
- Pain or pressure in the chest or abdomen
- Sudden dizziness
- Confusion
- Severe or persistent vomiting (vomiting that goes on)
- · Flu-like symptoms that improve but then return with fever and worse cough

Collection of ILI symptom presence and severity data for a sequential 7-day period using the FLUPRO questionnaire

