Email or text messages responses from subjects who report symptoms meeting the ILI case definition will trigger an email or text message to a study coordinator, who will then contact the subject to schedule a virtual acute ILI visit. Subjects who respond to the email/text message stating that they are experiencing ILI symptoms will be sent a web link to a 7-day ILI severity questionnaire that will record the severity of ILI symptoms that they experienced in the past 24-72 hours in the online questionnaire. They will also receive daily email/text reminders to enter the symptom severity information for the past 24 hours for each of the remaining six days.

ILI surveillance in military trainees/recruits

Internet/email/text message access is not available to military recruits/trainees, and therefore they will not complete the FLUPRO questionnaire should they develop ILI symptoms. As such, at enrollment they will be guided to report to sick call should they develop acute ILI symptoms during the study follow-up period. Study coordinators will be on hand at the appropriate medical clinic to obtain acute ILI Visit Day 1 data and specimen collection. A convalescent ILI visit is not required for military recruits /trainees. **ILI Visits have the option of taking place virtually or in-person**

VIRTUAL ILI VISIT PROCEDURES

Acute ILI Visit #1 : visit during an acute phase of ILI episode

Subjects who develop ILI symptoms will undergo the following procedures:

- Self-collected nasal swab specimen.
- Self-collected blood sample (40 µL)
- ILI History
- If hospitalized:
 - ILI hospitalization status
 - Number of days hospitalized (if hospitalized for care)
- Number of work/duty days absent related to ILI episode

Visit #2- Convalescent Visit (21-35 post trigger): visit during convalescent phase of ILI episode Subjects who develop ILI symptoms will undergo the following procedures:

- Self- collected blood sample (40 µL)
- If hospitalized
 - ILI hospitalization status
 - Number of days hospitalized (if hospitalized for care)
- Total number of work/duty days absent related to ILI episode

IN-PERSON VISIT PROCEDURES

Visit #1- Acute ILI Visit

Subjects who develop ILI symptoms will undergo the following procedures:

- Self-collected nasal swab specimen.
- CRC collected nasal swab specimen
- In-clinic self-collected blood sample (40 µL) or intravenous blood draw (16 mL) (subject's choice)
- ILI History
- If hospitalized
 - ILI hospitalization status

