Study data will be derived from source documents and then transcribed onto electronic CRFs (eCRFs). Study data may also be entered directly on the eCRFs as original observations and thus have the dual function of source document and data capture form at the study site. In the case where a source documentation is not completed on the CRF directly, the transcriptions will occur on an ongoing basis during the study in accordance with Good Clinical Practice (GCP) guidelines by study staff delegated this task on the Delegation/Responsibilities Log. Study staff should maintain in the regulatory files a list of CRFs that serve the dual purpose of source documentation and CRF.

DCC programmers will pull MDR records on enrolled subjects at the end of the influenza season (o r end of study, as applicable) in an attempt to confirm relevant health information, such as comorbidities, prescription medications, history of influenza and other vaccination history of influenza and other respiratory infections (i.e., influenza, SARS-CoV-2, and other respiratory pathogen test results), healthcare utilizations and costs associated with ILI. Evaluations mandated by this research protocol will have no impact on standard of care assessment and treatment.

Names and email will be collected prior to enrollment using the MHS Portal J6 email list. This will allow access to send recruitment materials along with e-consents to potential study participants.

Demographics: Following administration of informed consent, collected demographic data will include but not be limited to age, sex, DEERS status, and military rank.

Past Medical History: Information on subjects' past medical history will be captured at or after enro llment. The information collected will focus on comorbidities, history of influenza and other respiratory infections (e.g., SARS CoV-2), and history of influenza and other vaccinations. Medical history information will be collected via electronic or paper questionnaires, or through an MDR pull. Coordinators will review the subjects' questionnaire responses for completeness. Health information from up to five years prior to a subject's study enrollment may contribute to the MDR record data pull.

FluPRO daily symptom questionnaire information will be entered into a REDCap web form on a URL provided by the DCC. Subjects will be provided a direct link to access the website and enter their study data.

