During the influenza season, automated weekly email or text messages will be sent to subjects asking them if they have experienced ILI symptoms in the past 7 days. Subjects who meet the ILI case definition will be asked to complete an online 7-day symptom severity questionnaire and to schedule an acute ILI visit with a study coordinator. The questionnaire takes approximately 10 minutes to complete. At the acute ILI visit (Visit 1), study coordinators will record subjects' vital signs, ILI history, information on prescribed medications, hospitalization status, and work absences. They will also collect a nasal swab for diagnostic purposes and a blood sample for serologic studies and immune function. Subjects will contribute another blood specimen at a convalescent ILI visit approximately 28 days after the acute ILI visit (Visit 2). Information on ILI duration, hospitalization status, concomitant medications and work absences will be updated at this visit. Subjects will be monitored through as many ILI episodes as they experience, though subjects will only be compensated for the first 3 episodes. ILI episodes must be separated by at least 30 days. Information on ILI health care utilization and cost will be abstracted from the Military Health System Data Repository database by IDCRP study staff at the end of each influenza season.

Due to their lack of access to technology, participants who are Marine Corps recruits will not participate in the weekly surveillance; they will present when ill at the health clinic and nasopharyngeal and blood samples will be collected during Visit 1. Recruits are not required to schedule a Visit 2.

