5.1.5 Plan for handling missing data and extreme values

Data will come from multiple sources including an enrollment document and from medical records. Care will be taken to minimize missing data, but sometimes this will still occur. For each variable, the data managers will review the data and calculate the percent missing. In addition, extreme values will be

identified. Participants with missing vaccination or outcome data will be excluded. A sensitivity analysis will be performed using only those non-recruit participants with at least 50%/75% of the weekly survey data in order to ensure that findings are consistent.

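### For non-recruits, an illness that falls wholly inside an unanswered survey week is outside every later question, and no catch-up or self-report route is described

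*Protocol*

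**What the plan says.** - **Survey window.** Protocol 10.1 (Acute Influenza-like Illness Surveillance) has an automated message "at 1 week intervals asking them if they have experienced ILI in the preceding 7 days". SAP 3.1 uses the same window, "asking them if they have experienced ILI symptoms in the past 7 days".
- **Non-response.** "Subjects will get a reminder email or text 72 hours later and again 24 hours later if they have not responded". Nothing is described after the second reminder.
- **Trigger.** In Protocol 10.1, a reply that meets the ILI definition alerts the coordinator, who arranges the acute visit. No other reporting route is given for non-recruits. Recruits are handled separately: "at enrollment they will be guided to report to sick call should they develop acute ILI symptoms".
- **Endpoint and denominator.** SAP 4.1.1 requires RT-PCR on a swab taken at presentation with ILI. SAP 5.1.2 divides cases by the number vaccinated in each group.
- **Loss to follow-up.** Protocol 13.6 covers participants who answered no surveillance at all, or who reported ILI and then completed no ILI visit or procedure. Someone who skips some weeks is in neither group.
- **Other sources.** Protocol 9.1 seeks permission to "review their recorded medical encounters in order to ascertain whether they sought care for influenza-like illness". Protocol 10.2 pulls MDR records that include "influenza, SARS-CoV-2, and other respiratory pathogen test results". Protocol 10.1 plans end-of-study blood kits, partly to see whether cases were missed.
- **Sensitivity analysis.** SAP 5.1.5 repeats the analysis "using only those non-recruit participants with at least 50%/75% of the weekly survey data".

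**The concern.** The question has a fixed look-back and the swab depends on the answer. If a participant is ill from Tuesday to Friday, ignores that week's message and both reminders, and answers the next message, the new question covers only the newer seven days. The illness is not asked about, no swab is taken, and the participant counts as uninfected.

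Two things are at stake. The primary analysis is short of cases: Protocol 11.1 attributes low power to low attack rates, and the response was to raise the enrolment target from 15,000. The exploratory ILI frequency is also undercounted, whether or not a swab would have been positive.

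The plan also does not say whether the seven days run back from the date the message was sent or from the date of the reply, so the period covered by a late answer is undefined.

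**Working it through.** **1. Reproduce the plan's sample size.** Inputs from Protocol 11.5: attack rates 2.3% and 1.54%, one-sided alpha 0.025, power 0.80, 15% lost to follow-up, 6,000 per arm. Two-proportion formula, pooled variance under the null, no continuity correction:

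n = [1.960 × √(2 × 0.0192 × 0.9808) + 0.842 × √(0.023 × 0.977 + 0.0154 × 0.9846)]² / 0.0076² = 5,117 per arm.

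5,117 / 0.85 = 6,020, against 6,000 stated. The plan's figure reproduces. With 6,000 × 0.85 = 5,100 evaluable per arm, power is 79.9%.

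**2. Share of illnesses never asked about.** The documents give no weekly response rate, so r is an assumption. Suppose weeks are answered independently with probability r, onset is uniform within the week, and symptoms last d days (d ≤ 7). An illness is missed if its own week is unanswered and it either ends within that week or runs into a second unanswered week:

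missed = (1 − r) × [(1 − d/7) + (d/7)(1 − r)]

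| r | d = 3 | d = 5 | d = 7 |
|---|---|---|---|
| 0.80 | 13.1% | 8.6% | 4.0% |
| 0.75 | 17.0% | 11.6% | 6.3% |
| 0.50 | 39.3% | 32.1% | 25.0% |

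The formula credits illnesses that continue into the next answered week as caught. It takes no account of illnesses found through medical records.

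**3. How late a recovered swab would be.** An illness missed by a seven-day window ended more than 7 days before the next answered message. Its onset was therefore more than 7 + d days before that message: over 10 days for d = 3, 12 for d = 5 and 14 for d = 7. A simulation of the model in step 2 (r = 0.75) gave minimum intervals of 10, 12 and 14 days and medians of about 13, 15 and 19 days. The endpoint is RT-PCR on a swab from the acute visit, so a longer look-back alone can be expected to recover few primary-endpoint cases.

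**4. What can still be changed.** Protocol 11.1 reports 10,771 participants enrolled in the first three seasons. That leaves 18,000 − 10,771 = 7,229, or 40% of the total, in the fourth. Capturing 5% or 10% more cases in that season adds about 2% or 4% to the trial's cases. Expected cases at 5,100 per arm are 117.3 (egg) and 78.5 in each comparator, 274 in all, so the gain is about 5 to 11 cases.

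**5. Effect on power, per pairwise comparison.** On the log-RR scale, SE = √(1/117.3 + 1/78.5 − 2/5,100) = 0.1444, ln(0.023/0.0154) = 0.401, and power = Φ(0.401/SE − 1.96).

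| Cases | Log-RR method | Two-proportion method |
|---|---|---|
| As planned | 79.3% | 79.9% |
| 2% more | 80.1% | 80.7% |
| 4% more | 80.9% | 81.4% |

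The gain is roughly 1 to 1.5 points.

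**6. Direction.** If capture is c in every arm, the observed ratio is (c × 1.54%) / (c × 2.3%) = 0.67, unchanged. Equal loss costs power only.

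**The case against.** The strongest reply is that the plan accepts imperfect ascertainment and has other ways to look for cases. Protocol 11.1 calls the trial pragmatic and relies on incentives to be assessed. Medical encounters are reviewed, MDR test results are pulled, blood kits look for missed cases, and a survey-completeness sensitivity analysis is planned.

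These provisions matter, but they are not stated to recover primary-endpoint cases. Neither record source is named as feeding the endpoint, and both reach only people who sought care. Protocol 11.1 expects perhaps 30% of those with ILI to do so, and notes that test types vary between clinical laboratories. The kits are limited to about 1,000 participants who reported at least one ILI, so they cannot show someone whose only illness fell in an unanswered week. The sensitivity analysis subsets participants and adds no case.

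The reply does stand against several stronger readings that a reader might infer:

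- **Late answers lose the week.** The reminders exist to obtain a late answer. Days are lost only if the seven days run back from the reply. In that case a reply at 96 hours would leave about the first 4 days uncovered, but the documents do not state the anchor.
- **Every illness in an unanswered week is lost.** Illness continuing into the next answered week is asked about, and medical records may show others. Recruits are not on the survey.
- **The 50%/75% cut-offs show that many missed weeks are expected.** They set a sensitivity analysis and say nothing about how often weeks are missed.
- **Power falls from about 80% to 78% or 75%.** With 5% or 10% of cases removed throughout, the two-proportion power would be 77.8% or 75.5%. But the planning rates were set after three seasons observed under this same survey, so missed weeks are probably already in the 2.3%. Subtracting them again would double count.
- **The relative risk is biased.** The trial is open label, so different response by arm is possible, but nothing in the documents shows it.

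**Conclusion.** The gap is real and minor. For non-recruits, an illness wholly inside an unanswered week falls outside every later survey window, no catch-up follows the reminders, and the participant is counted as a non-case unless another route finds the illness. Whether an MDR positive would then count towards the primary endpoint is not stated.

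The achievable gain is at most about 1 to 1.5 points of power. It assumes 5-10% more influenza cases captured among fourth-season participants, all of them PCR-positive. The 5-10% is itself an assumption, since no response rate is given. Nearly all of that gain would have to come from reporting during acute illness, not from a longer look-back. The longer look-back mainly makes the ILI count more complete.

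**What to change.** 1. Put a standing 'report symptoms now' link in every weekly message and reminder, starting the same ILI workflow, so that swabs can be taken during acute illness whether or not the weekly question was answered.
2. Ask about symptoms 'since you last answered on [date]'. This closes the gap left by unanswered weeks and fixes the anchor for late replies. Its main value is a more complete ILI count.
3. Use the onset date already recorded at ILI Visit 1 (Protocol 10.2) to flag late swabs in the analysis.
4. State in the SAP whether influenza positives found only in MDR records count towards the primary endpoint.

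The cost is an edit to the automated REDCap messages and a short amendment. The downsides are longer recall, some uninformative late swabs, and fourth-season ascertainment that differs from the first three seasons. That difference would apply equally to the randomised arms within the season. The link also depends on participants who may already be ignoring messages, so its yield is uncertain.

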11.0 Statistical/Data Analysis Plan

11.1 Statistical Considerations:

List the statistical methods to be used to address the primary and secondary objectives, specific aims, and/or research hypotheses. Explain how missing data and outliers will be handled in the analysis. The analysis plan should be consistent with the study objectives. Include any sub-group analyses (e.g., gender or age group). Specify statistical methods and variables for each analysis. Describe how confounding variables will be controlled in the data analysis

The statistical plans discussed below are not final or definitive. They will need to evolve as the flu seasons develop and we communicate with other ILI study centers and the sponsors. In case of

a severe epidemic, they may have to change substantially. Detailed statistical protocols will need to be created for the specific studies that will fulfill secondary objectives. The statistical considerations below for the secondary objectives will serve as starting points for the more detailed statistical plan.

Primary Aim

Specific Aim #1: Comparison of the effectiveness (prevention of laboratory-confirmed influenza illness) of three types of licensed seasonal influenza vaccines.

Research question: Is either the cell-culture based vaccine or the recombinant vaccine more effective than egg-based vaccine? There are two hypotheses of interest based on influenza attack rates (AR): Vaccine Effectiveness (VE)= $(\underline{AR}_0 - \underline{AR}_1) \times 100\% = (1-\underline{AR}_1/\underline{AR}_0) \times 100\% = (1-\underline{RR}) \times 100\%$

AR₀

when AR_0 is placebo, VE~= vaccine efficacy or via Nauta ("absolute vaccine efficacy") when AR_0 is the egg-based vaccine then the VE~= *relative* vaccine efficacy.

We want relative VE of 33% => $1 - AR_1/AR_{egg} = 0.33$, therefore 1- 0.33 = $AR_1/AR_{egg} = RR$ therefore 0.67 =RR (AR1 = attack rate in either cell-culture based or recombinant vaccine)

We have simplified the primary hypotheses for the study and have opted for two pairwise comparisons rather a single three-way comparison. There are two hypotheses of interest based on influenza attack rates (AR):

H₀: RR=1 vs H_A: RR < 1; alpha=0.025;

The RR to be tested is defined as: 1) RR1=AR_{cell} / AR_{egg} and 2) RR2=AR_{recombinant} / AR_{egg} Text: Statistics in Clinical Vaccine Trials by Jozef Nauta.

1. Endpoint:

Influenza attack rates in the egg-based, cell-culture-based, and recombinant protein influenza vaccines arms of the study in the 2018-2019, 2019-2020, 2020-2021, and 2021-2022 seasons.

2. Ascertainment of primary outcome:

Laboratory-confirmed influenza as ascertained by a sensitive and specific assay is needed to assess effectiveness. The best assay is RT-PCR from nasopharyngeal swab specimens (various assay platforms); one particular antigen detection assay has similar sensitivity and performance characteristics, but numerous available rapid antigen detection tests for influenza are poorly sensitive and have poor negative predictive value, thus risking false-negative results if relied upon for outcome. There is heterogeneity across MHS clinical laboratories with respect to the type of test that is employed. A key factor is that individuals must present for care to have outcome ascertainment. Thus, follow-up methodology will involve strategies to increase likelihood of presentation for evaluation of incident ILI following vaccination.

3. Statistical analysis:

Incidence rates: To determine incidence, we will use the number of enrolled laboratoryconfirmed influenza cases by vaccine formulation as the numerator. For the denominator, we will use the number of enrolled subjects by vaccine formulation. We estimate that approximately 30- 40 percent of the subjects and will develop ILI symptoms. Of this group, perhaps 30 percent will seek care, with symptom severity the leading predictor for seeking care. We realize that there is no effective way in a large study to avoid the potential for bias in case ascertainment due to differences in symptom severity. As a pragmatic study, our goal is not to eliminate bias but to minimize the impact of bias , by using a broad but standardized case definition and by providing incentives for symptomatic individuals to be assessed. We can also use symptom severity data from the FLUPRO questionnaire to explore the extent to which symptom severity scores differs by region.

The ability of the study to detect a difference in effect is proportionate to the incidence of the outcome. A total of 172 influenza cases were reported among the 10,771 subjects enrolled in first three years of the study (2018-2021). The influenza attack rate has ranged from 0% in third season (COVID-19 pandemic), to 2.5% in the second season, with an overall attack rate 1.6% The observed attack rates are lower than baseline attack rates of 5% and 3% that formed the basis of sample size calculations for the first three years of the study. Consequently, the power to detect significant differences in VE between vaccine arms has been too low to due to the low attack rates. For the fourth year of the study is to increase the enrollment target from 15,000 to 18,00 to enhance power to detect significant differences in VE between attack rates are lower.

Secondary Aims:

Specific Aim #2:

Determine whether cell-culture-based and egg-based influenza vaccines give comparable HI and PVN titers to egg- and cell-matched vaccine antigens. An outcome of this objective is the potential to determine whether cell-culture-based vaccine antigens can provide broader coverage of circulating viruses than egg-based vaccine antigens.

Research Question: Is the proportion of subjects who seroconvert in either the cell-culture based or recombinant vaccine arm of the study greater than in the egg-based vaccine arm of the study.

There are two hypotheses of interest for Specific Aim 2, based on the seroconversion rates (SCR)

H₀: RR=1 vs H_A: RR < 1; p=0.025; The RR to be tested is defined as: 1) RR1=SCRcell / SCRegg and 2) RR2=SCRrecombinant / SCRegg

1. Endpoints:

- Humoral responses: HAI titer, anti-NA titer, virus-neutralizing titer
- Cellular responses (exploratory): frequency of antigen-specific CD4 and CD8 cells, B cells

SA 2.1: To obtain post-vaccination sera panels to determine breadth of reactivity to circulating strains.

This will be accomplished by recruiting consenting adults to an IRB-approved study conducted during a routine influenza vaccination campaign, collecting sera up to 30 days before and 21-35 days after vaccination with egg- or cell-culture-based or recombinant influenza vaccines. The samples will be de-identified and shipped to partner laboratories for aliquoting, storage, and antigenic analyses. We intend the study to be conducted during early vaccination campaigns performed at DoD facilities.

SA 2.2: To identify individuals who responded to H1N1, H3N2, B/Victoria and B/Yamagata vaccine components. This will be accomplished by testing pre- and post-vaccination sera for HA inhibition (HI) and pseudovirus microneutralization (PVN) antibody titers. Individuals who had a 4-fold or greater response against each matched antigen in the vaccine will be considered responders (i.e. if egg-based vaccine, the test will be conducted against egg-based antigen). The study will be designed to identify responders to egg- and cell-culture-based vaccines for each vaccine antigen (H1N1, H3N2, B/Yamagata and B/Victoria). For H3N2 strains that do not hemagglutinate, only PVN titers will be determined. The sera collected postvaccination from responders will be aliquoted and distributed to laboratories performing assays to evaluate the breadth of antibody reactivity.

SA 2.3: To evaluate differences in serum reactivity between egg- , cell-culture-based and recombinant antigens.

We will test pre- and post-vaccination sera against antigens with sequences corresponding to the "other" platform. We will compare PVN antibody titers against egg- and cell-culture-based antigens for all strains included in the vaccine, and calculate the response rate (i.e. percent of individuals in each arm with a 4-fold or greater titer response) of each arm of the study against egg and cell antigens. The results from this test will indicate whether antibodies elicited in response to egg- and cell-culture-based vaccines are specific for the immunogen.

SA 2.4: Compare the breadth of the antibody response elicited by egg, cell-culture-based and recombinant vaccines to circulating strains.

To determine the breadth of antibody reactivity, post-vaccination serum PVN titers will be measured against cell-culture-based vaccine and emerging circulating virus antigens representing most clades from each subtype. Only cell-based sequences will be used in this analysis because these are representative of the original human isolate sequences. We

propose to include the HAs of at least 6-10 recent virus isolates per subtype/lineage. PVN titers against recent virus isolates that are >4 fold different from the homologous vaccine antigen will be considered low reactors (LRs). The breadth of reactivity will be scored by calculating the number of LRs identified for each study subject, e.g., sera that react to all antigens will be given a score of 100%, sera that react to no antigens will be given a score of 0% and sera that react to 4 of 10 antigens will be given a score of 40%. The overall breadth of reactivity for each study Arm will be calculated as the average breadth of reactivity for all persons in the Arm. If the difference between the groups is not significant, additional antigens within the subtype/lineage but that are known to be antigenically-distinct, may be tested.

SA 2.5: To examine the breadth of reactivity against past strains.

Recent studies demonstrate a back-boost effect following vaccination, i.e. increased antibody titers against influenza antigens from past vaccines or infections. The human immune responses are therefore impacted by prior vaccination history or infection. To retain the possibility of performing additional tests that examine the back-boost effect, left over sera will be stored for future additional investigations of how pre-existing breadth of antibody reactivity to past influenza strains influences responses to current influenza vaccines.

Exploratory Aims:

Specific Aim #3: To determine if the impact of the influenza vaccine on disease burden and the attributable healthcare costs differs by product type.

An analysis of the impact of ILI and SARI on health care utilization will allow a more detailed estimation of the burden of infections caused by these pathogens in military populations. The collection and analysis of health care utilization information will be useful for informing priorities for ARI control and will serve as a basis for the comparison of the effectiveness of different ILI control measures to enhance Force Health Protection.

Endpoints:

- Incidence of PCR-confirmed influenza cases
- Frequency of influenza-confirmed hospitalization
- Frequency of influenza-like illness
- Work days lost due to influenza
- Work days lost due to influenza-like illness
- · Healthcare costs/utilization attributable to influenza
- · Healthcare cost/utilization attributable to influenza-like illness

Specific Aim #4: To evaluate the association host single nucleotide polymorphisms (SNPs) on the immune responses to the influenza vaccine and on influenza severity

Endpoints:

- Frequency of SNPs by seroconversion status
- Frequency of SNPs by geometric mean titer (GMT) cutoff
- Frequency of SNPs by mean fold rise (MFR) cutoff
- Frequency of SNPs by influenza status
- Frequency of SNPs by influenza severity classification

11.2 Sample Size:

18000

11.3 Total number of subjects requested (including records and specimens):

18000

11.4 If you are recruiting by study arm, please identify the arms of the study and how many subjects will be enrolled in each arm

Arm 3: egg-based influenza vaccine, 6,000.

Sub-study: Approximately 1,200 subjects total recruited from the main study population.

